### **Study Drug Dispensation and Distribution**

If a patient is not able to attend a clinic visit, to ensure the continuity of providing patients' study drug within the constraints imposed by the pandemic (or other global crisis), the site staff may decide to supply study drug to patient as follows:

- Adequate supplies of study drug can be shipped to the patient by the study staff using a third-party service with approval from the patient. The third-party vendor will be agreed upon with the sponsor.
- The patient may request, with prior arrangement/agreement with the site, an authorized individual (a relative or delegate) to retrieve the study drug from the study site if the patient is unable to personally to do so.

### **Clinical Trial Monitoring**

Study monitoring visits may be postponed; however, the site monitor will continue to employ off-site monitoring practices such as routine communication methods (e.g., phone

Study Number: INVEX-CLIN-IIH-301 Protocol	Compound No.: Presendin
	Version: 3.0

calls, emails, video visits) with the sites to get information on study progress, patient status, and information on issue resolution as detailed in the Data Monitoring Guidelines, Remote source data verification.

If the trial site monitor cannot be on-site to carry out the final drug accountability for reconciliation purposes, and the operation cannot be postponed, it may be carried out by a pharmacist from the site pharmacy or by the study coordinator/data manager with suitable training. The study drug can be returned to the sponsor by the site pharmacy directly, or destroyed in accordance with local practices, if applicable, and with sponsor approval.

### **Direct Contracts with Third Parties/Specialized Service Companies**

If necessary, direct contracts can be established with third-party local physicians to conduct activities related to the clinical management of patient for whom the investigator is responsible and maintains oversight. In such situations, the investigator is required to provide the local physician with a delegation letter listing all delegated activities. The sponsor, through the study investigator or institution, will reimburse the local physician for the test/procedures conducted outside of the standard of care.

Clinic visits should take place to the extent possible and usual protocol requirements adopted for all subjects as soon as the crisis-related limitations permit.

All safety data that are possible to obtain locally should be collected at a remote visit. These measurements may include the use of local practitioners and resources.

Exceptional measures taken in response to a crisis (e.g., COVID-19) and their impact on study results, such as tests done in a local laboratory, will be explained, assessed and reported in the clinical study report following ICH E3 guidance.

## **8. LIFESTYLE AND/OR DIETARY RESTRICTIONS**

Patients will receive lifestyle advice as per routine care from their treating physician.

## **9. INVESTIGATIONAL PRODUCT**

### **9.1. Dosage and Administration**

#### **9.1.1. Randomised Period**

During the 24-week randomised treatment period ([Figure 1](#)) patients will be randomised in a 1:1 ratio to receive active treatment or placebo.

Either

Study Number: INVEX-CLIN-IIH-301 Protocol	Compound No.: Presendin
	Version: 3.0

Presendin (2.0mg exenatide) as a SC injection, self-administered once weekly.

Presendin is supplied as 2 parts, one vial consisting of a drug part (white or grayish white powder in a clear vial) and one pre-filled syringe containing the diluent part (colourless liquid). The drug part is suspended in the diluent part solution and administered as a suspension.

or

Placebo as a SC injection, self-administered once weekly.

Placebo is supplied as 2 parts (visually identical to the Presendin vial and pre-filled diluent syringe). The drug part will exclude the active pharmaceutical ingredient (exenatide acetate) and the diluent part will be the same as the active treatment diluent. The drug part is suspended in the diluent part solution and administered as a suspension.

## 9.2. Dose Rationale

The proposed 2mg weekly dose was based on the pharmacokinetic performance of the Pepton formulation (PT320). Pharmacokinetic profiles obtained after repeated once weekly dosing of 2mg of PT320 s.c. (as specified in the Presendin IB phase 2 clinical study in patients with type 2 diabetes) were comparable to those predicted by the population PK model developed for weekly s.c. administration of the recommended dose of the 2mg Bydureon extended-release formulation [Cirincione 2017], with time to reach the steady state slightly shorter for PT320 than for Bydureon (7-8 weeks vs 8-10 weeks) and with steady state plasma concentrations remaining within a comparable range for both products. Based on the same molecule and dose, comparable plasma concentrations for PT320 and Bydureon and the established safety profile of Bydureon a similarly acceptable safety and tolerability profile for PT320 is expected.

## 9.3. Maintaining the Blind

This is a double-blind trial.

A computer/website system will be used to maintain the blind for this trial. The site will be provided with website login details for the system. If the Investigator needs to unblind a patient's treatment, due to a medical emergency, the website should be accessed to unblind for that patient. .

The responsibility to break the treatment code in emergency situations resides solely with the investigator.

Study Number: INVEX-CLIN-IIH-301 Protocol	Compound No.: Presendin
	Version: 3.0

#### **9.4. Treatment Assignment**

Patients will be randomised in a ratio of 1:1 to receive active treatment (Presendin) or placebo. A computer/website system will be used to randomly assign each patient to a treatment arm.

#### **9.5. Packaging and Labelling**

Individual supplies of trial medication will be provided to the sites in a double-blind format. The labels will contain all information required to meet the applicable local regulatory requirements.

Further information on packaging, labelling and dispensing are included in the Pharmacy Manual.

#### **9.6. Preparation**

Each dose of trial medication is provided as two parts, a single use vial and a pre-filled syringe of diluent. Patients will receive training and be provided with an instruction sheet with details, on how to store, prepare, self-administer and discard/keep used trial medication.

#### **9.7. Handling and Storage**

Presendin, the active trial medication, contains the active ingredient, exenatide, which is hygroscopic and light sensitive and must be protected from light during storage. Prior to use, all trial medication should be stored refrigerated at 2-8°C.

#### **9.8. Product Accountability and Assessment of Compliance**

In accordance with International Council of Harmonisation – Good Clinical Practice (ICH-GCP), each trial centre will account for all supplies of trial medication. Details of receipt, storage, assembly, and return will be recorded. The unit of accountability will be one single active or placebo vial. Needles will be disposed of in a sharps box.

All unused supplies will either be destroyed or returned to the trial Sponsor at the end of the trial in accordance with instruction by the Sponsor.

All trial medication will be self-administered by the patients. If a dose is not administered as planned, patients will record the missed dose in their electronic/paper diaries and it will be documented in the electronic case report form (eCRF).

Study Number: INVEX-CLIN-IIH-301	Compound No.: Presendin
Protocol	Version: 3.0

## 9.9. Treatment of Investigational Product Overdose

Definition of Overdose: More than 1 (one) dose in 24 hours.

In the event a patient overdoses on trial medication the Investigator should be notified as soon as possible. If symptoms appear, the Investigator will treat the patient according to their clinical judgement depending on the type of clinical signs and symptoms exhibited by the patient. The Sponsor should be notified in writing within 24 hours of the Investigator becoming aware.

Effects of overdose that may be seen include severe nausea, severe vomiting and rapidly declining blood glucose concentrations.

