	V1 Clinic	V2 Clinic Baseline	V3 TC	V4 Clinic	V5 Clinic	V6 Clinic	V7 Clinic	V8 Clinic	V9 Clinic	V10  Clinic		Unscheduled repeat visual assessments 
Visit Window (days)		+3	± 1	± 3	± 3	± 5	± 5	± 5	± 5	± 14		± 5
Month	0	0			1	2	3	4	5	6		
Week	-1	0		2	4	8	12	16	20	24		29
Day	-7	1	3	15	29	57	85	113	141	169		204
Pharmacokinetic (PK) sampling 		X 		X	X	X	X	X	X	X		
Anti-Drug Antibodies (ADA) sampling		X		X	X	X	X	X	X	X		
Lumbar Puncture 										X 		
Trial medication training 	X	X										
Randomisation		X										
Trial medication Dispensing	X	X			X	X	X	X	X			
Trial medication Accountability				X	X	X	X	X	X	X		

 The screening period must be a minimum of 7 days, up to a maximum of 10 days. Patients who do not meet the eligibility criteria based on diary review at randomisation/baseline (e.g., too few headache days or unacceptable concomitant medication use) will be considered screen failures; however, if the patient wishes and the Investigator is in agreement, he/she can be re-screened as a new patient. If the screening period exceeds 7 days, then eligibility will be based on the last 7 days of the screening period, i.e., the 7 days prior to randomisation visit. Trial site research team should review diaries remotely on a weekly basis to ensure compliance and follow up any patients with missing data

 Vital signs to include: blood pressure and heart rate

 Women of child-bearing potential. Serum pregnancy test to be conducted at screening, thereafter, highly sensitive urine pregnancy tests will be conducted. Visit 11 urine pregnancy test may be conducted at home

 Frisén grade will be evaluated locally and the presence of papilloedema verified by the OCT Reading Centre at screening to confirm eligibility. Indeterminate cases should be referred to the IAC (and supplemented with fundus photography and ultrasound scan of the optic nerve) to confirm papilloedema prior to randomisation visit

 Haematology, coagulation, biochemistry and urinalysis

 All actual sampling times and dosing times will be recorded

 Baseline Post-dose PK blood sample

Study Number: INVEX-CLIN-IIH-301 Protocol	Compound No.: Presendin
	Version: 3.0

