#### **1.1.1. Name and Description of the Investigational Product**

Patients will receive active treatment, Presendin, or matching placebo.

Presendin is a modified release formulation of exenatide. Exenatide is a GLP-1 receptor agonist currently used in the management of type 2 diabetes. Presendin consists of a drug

Study Number: INVEX-CLIN-IIH-301 Protocol	Compound No.: Presendin
	Version: 3.0

part (white or greyish white powder in a clear vial) and a diluent part (colourless liquid in a pre-filled syringe). The drug part is suspended in the diluent part solution and administered as a suspension. The patient or responsible person will be responsible for rehydrating the product for injection. Presendin is administered as a once weekly SC sustained-release injection containing 2.0 mg exenatide. Matching placebo will also be supplied as 2 parts, as visually identical vial and pre-filled syringe. The drug part will exclude the active pharmaceutical ingredient (exenatide acetate) and the diluent part will be the same as the active treatment diluent. Placebo is administered once weekly as a SC injection.

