### **6.1.4. Visits 4, 5, 6, 7, 8 and 9 Clinic visits**

- Concomitant medication review
- Headache preventative medication review
- Headache diary review
- Vital signs (triplicate readings for blood pressure and heart rate will be taken at 1-minute intervals)
- Body weight and BMI (not visit 4)
- Adverse event review
- Targeted physical examination (visit 6, 8 and 9 only)
- Urine pregnancy test for women of child-bearing potential
- Electrocardiogram
- Visual Assessments to both eyes
  - Optical coherence tomography Imaging
    - Sites should initially check the scan quality. The OCT scan should then go through the upload processes to the OCT Reading Centre, without delay. The OCT scan will then be reviewed by the OCT Reading Centre for a full quality assessment. The report from the OCT Reading Centre will be sent to the site. Where the OCT is of insufficient quality it should be repeated as soon as possible at an unscheduled visit. Where the OCT processing is of insufficient quality it should be reprocessed as soon as possible by the site.

Study Number: INVEX-CLIN-IIH-301 Protocol	Compound No.: Presendin
	Version: 3.0

- Humphrey Visual Field (24-2 SITA-Standard)
  - Sites should initially check the performance quality of the HVF (to ensure no more than 15% false positives). The HVF should then be uploaded to the Visual Field Reading Centre without delay (an initial quality assessment takes place during the upload procedure). The HVF will then be reviewed by the Visual Field Reading Centre for a full quality assessment. The report from the Visual Field Reading Centre will be received by the site. Where the visual field is of insufficient quality it should be repeated at an unscheduled visit without delay.
- Visual Acuity (LogMAR score)
- Patient reported outcomes: VFQ-25 & 10-item supp, HIT-6, SF-36 and EQ-5D-5L in diary (not visit 4)
- Health Utilisation Form
- Laboratory assessments
- Pharmacokinetic blood sampling
- Anti-Drug Antibodies blood sampling
- Trial medication dispensing (not Visit 4) and accountability - patients should be reminded by the trial site to self-administer the trial medication weekly and to return used and unused trial medication at clinic visits

### 6.1.5. Visit 10

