In the 4 weeks prior to visit 10, patients must not have missed more than one dose of trial medication and must have self-administered their final dose within 7 days of visit 10. Patients will be reminded by the trial site to self-administer trial medication weekly, to continue this until the completion of visit 10 and to bring their trial medication with them at visit 10 for return.

Where more than one dose has been missed during the 4 weeks preceding visit 10, visit 10 should be delayed. Self-administration of trial medication should continue at 7-day intervals and then visit 10 rescheduled to ensure no more than one dose of the trial medication has been missed in the previous 4 weeks. Visit 10 should be delayed no more than 14 days.

- Concomitant medication review
- Headache preventative medication review
- Headache diary review

Study Number: INVEX-CLIN-IIH-301 Protocol	Compound No.: Presendin
	Version: 3.0

- Vital signs (triplicate readings for blood pressure and heart rate will be taken at 1-minute intervals)
- Body weight and BMI
- Adverse event review
- Targeted physical examination
- Urine pregnancy test for women of child-bearing potential
- Electrocardiogram
- Visual Assessments to both eyes
  - Optical coherence tomography Imaging
    - Sites should initially check the scan quality. The OCT scan should then go through the upload process to the OCT Reading Centre, without delay. The OCT scan will then be reviewed by the OCT Reading Centre for a full quality assessment. The report from the OCT Reading Centre will be sent to the site. Where the OCT is of insufficient quality it should be repeated as soon as possible at an unscheduled visit. Where the OCT processing is of insufficient quality it should be reprocessed as soon as possible by the site.
  - Humphrey Visual Field (24-2 SITA-Standard)
    - Sites should initially check the performance quality of the HVF (to ensure no more than 15% false positives). The HVF should then be uploaded to the Visual Field Reading Centre without delay (an initial quality assessment takes place during the upload procedure). The HVF will then be reviewed by the Visual Field Reading Centre for a full quality assessment. The report from the Visual Field Reading Centre will be received by the site. Where the visual field is of insufficient quality it should be repeated at an unscheduled visit without delay.
  - Visual Acuity (LogMAR score)
- Lumbar puncture (within 7 days of last dose of trial medication)

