#### **6.2.2.4.6. Pharmacokinetic sampling**

Pharmacokinetic sampling is to characterize the pharmacokinetics of exenatide after once weekly subcutaneous administration of Presendin at the times outlined in the Time and Events table ([Table 1](#)).

The primary purpose of the pharmacokinetic sampling is to characterize the steady state concentrations of exenatide. All actual sampling times and dosing times will be recorded.

Sampling and processing will be performed as described in the Laboratory Manual.

Study Number: INVEX-CLIN-IIH-301 Protocol	Compound No.: Presendin Version: 3.0
---	--

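### In protocol v3.0, the 24-hour overdose window in section 9.9 does not fit a once-weekly sustained-release injection, so an early extra dose does not trigger the prompt sponsor notice

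*Protocol*

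**What the plan says.** Section 9.9 of protocol v3.0 (effective 08-Jun-2022) gives the rule as "Definition of Overdose: More than 1 (one) dose in 24 hours". The duties that follow apply when a patient overdoses: the investigator is to be told promptly, any symptoms are treated on clinical judgement, and "The Sponsor should be notified in writing within 24 hours of the Investigator becoming aware".

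The product and schedule are fixed elsewhere. Section 1.1.1: "Presendin is administered as a once weekly SC sustained-release injection containing 2.0 mg exenatide". Section 9.1.1: "Presendin (2.0mg exenatide) as a SC injection, self-administered once weekly". The Visit 10 instructions (6.1.5) confirm the spacing: "Self-administration of trial medication should continue at 7-day intervals". Section 9.2 gives 7-8 weeks to steady state on weekly dosing.

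Protocol v1.0 carried the same written-notice duty in its section 9.9 but did not define overdose; v3.0 has the definition. The file also holds appendix pages headed v4.0, but not the body of that version.

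**The concern.** A limit of one dose per day suits a product dosed daily or more often. Here the planned spacing is a week and the drug is released slowly. A patient who injects a second full dose two or three days early has departed clearly from the regimen, yet under 9.9 no overdose has occurred and the notice that the sponsor chose to require does not apply.

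All doses are self-injected, and Table 1 has medication dispensed at weeks 0, 4, 8, 12, 16 and 20, so patients hold several doses at home. Section 9.9 lists severe nausea and vomiting and a fast fall in blood glucose as effects of overdose. The glucose effect weighs less in this trial, because section 1.2 ties hypoglycaemia to other glucose-lowering drugs and patients using those are excluded. What is at stake is how soon the sponsor hears of a non-serious early repeat dose once the investigator knows of it.

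**Working it through.** The plan gives no figure to reproduce. The check is interval arithmetic plus a reading of the other provisions.

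**Inputs.** Overdose window 24 h (9.9). Dose 2 mg (1.1.1, 9.1.1). Interval 7 days = 7 × 24 = 168 h (6.1.5). Compliance limit above 125% of scheduled doses (11.2.1). Scheduled doses: 24, assuming one per week at weeks 0 to 23.

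**Step 1: share of the interval.** 24/168 = 14.3% lies inside the window and 144/168 = 85.7% outside.

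**Step 2: two extra doses compared.** An extra dose at 23 h and one at 48 h each bring the total to 2 × 2 = 4 mg, against 2 mg planned per 168 h. The first is an overdose with written notice; the second is neither. They differ by 48 − 23 = 25 h. With 7-8 weeks to steady state, successive doses must overlap, so exposure in the two cases should be similar. That is inference: the documents give no concentration curve for an early repeat dose.

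**Step 3: does another provision supply the notice?**

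| Provision (v3.0) | What it does | 24-hour notice of an early extra dose? |
|---|---|---|
| Table 1, footnote 1: "Trial site research team should review diaries remotely on a weekly basis to ensure compliance" | May reveal it | No |
| 6.2.2.4.6: "All actual sampling times and dosing times will be recorded" | May reveal it | No |
| 6.1.4: "Trial medication dispensing (not Visit 4) and accountability" | Vial counts at visits may reveal it | No |
| 9.8 diary rule | Names only missed doses | No |
| 11.2.1 compliance limit | Cumulative; leads to withdrawal from treatment | No |
| 12.1.3 AEs and special situations | Reported; the latter undefined, no time limit stated | No |
| 12.2.3 SAEs | 24-hour report | Only if an SAE follows |

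**Step 4: the compliance limit.** One extra dose gives 25/24 = 104.2%. The limit is 1.25 × 24 = 30 doses, so it is passed only at 31, which is 7 extra.

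**Step 5: what a minimum spacing would do.** A spacing of 48, 72 or 120 h covers 48/168 = 28.6%, 72/168 = 42.9% or 120/168 = 71.4% of the interval. A patient who takes a missed dose *d* days late and then returns to the usual day leaves 7 − *d* days between doses. That meets the spacing for *d* up to 7 − 48/24 = 5, 7 − 72/24 = 4, or 7 − 120/24 = 2 days. If the rule says less than 48 h, a dose at exactly 48 h still falls outside.

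**The case against.** The strongest reply has four parts. First, the sentence is in v3.0, a v4.0 exists, and its section 9.9 cannot be seen. Second, 9.9 is a clear rule that no other section contradicts, and it is more definite than v1.0, which left overdose undefined. Third, the documents give no toxicity threshold, no exposure data for an early repeat dose and no rate of such dosing; overlapping doses may even mean that one extra injection at steady state adds only modestly to exposure. Fourth, diary review, recorded dosing times, vial counts and AE reporting make it likely that early dosing comes to light, while a spacing set close to 7 days would label legitimate catch-up doses as overdoses.

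Most of this stands as a limit on size. It does not remove the point: none of the other routes carries the 24-hour written notice, and clear wording does not make the window fit the schedule.

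A reader might infer that early repeat dosing goes unmonitored, or that patients lack a safety control. The documents do not support that: several checks may reveal it, and any resulting AE or SAE is reported in the usual way. A reader might also take 86% as a measure of risk; it is only the share of the week outside the window.

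**Conclusion.** The point holds for v3.0, as a minor one. The definition does not match a weekly sustained-release product, and an unplanned extra full dose more than 24 hours but only a few days after the last one does not trigger the section 9.9 notice. The loss is confined to prompt sponsor notice of non-serious early repeat dosing. AE and SAE capture, sample size, power and the efficacy analysis are unaffected.

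The conclusion rests on the literal wording of 9.9 and on the v3.0 text. It extends to v4.0 only if that version keeps the sentence. The clinical importance of a dose two to six days after the last one cannot be judged from the documents.

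**What to change.** If v4.0 keeps the sentence, reword 9.9 so that overdose means either more than one dose in 24 hours, or any dose beyond the weekly schedule taken less than a stated minimum spacing after the previous one. A spacing of 72 h could serve as a starting value. It is an assumption, to be confirmed by the sponsor's medical team from the Investigator's Brochure within a range of about 48 to 120 h. Exclude a documented catch-up of a missed dose that respects the spacing; at 72 h this leaves room for a dose up to 4 days late followed by a return to the usual day. Keep the existing 24-hour written notice. In 9.8, have patients record extra or early doses as well as missed ones.

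The cost is a sentence or two in each section, a site memo and a few more overdose reports to process. A spacing near the upper end of the range would catch more early doses, but would also bring more catch-up dosing into the definition.
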